1.0 Background

Inability of the surgeon to identify or localize the diseased PG can occur in 5 – 10% of cases resulting in failed parathyroidectomies (1, 2). As a result, persistent hyperparathyroidism can occur in these patients resulting in unnecessary repeat surgeries that may be associated with increased morbidity and costs (3, 4). Ultrasound imaging, ^{99m}Technetium-sestamibi scintigraphy, and computed tomography (CT) have so far demonstrated variable efficacy in preoperative localization of diseased PGs (5, 6) and may not always correlate well with the surgical field of view as observed intraoperatively. Consequently, most surgeons rely on visual identification of PGs during surgery, whereby the accuracy of PG identification is eventually determined by her/his surgical skill and experience (7, 8). When in doubt, a surgeon routinely confirms the identity of PG tissue intraoperatively by sending the specimen for frozen section analysis (or PTH aspirate) that typically requires a wait time of 20–30 minutes per sample (9) and has additional costs.

By easily being able to distinguish parathyroid from other tissues intraoperatively, postsurgical complications and associated costs may be reduced. The unique discovery of near infrared autofluorescence (NIRAF) in parathyroid tissues demonstrated that optical modalities that detect NIRAF can be utilized for non-invasive and label-free identification of parathyroid tissues with an accuracy as high as 97%.(10, 11, 12, 13) Since then, several research groups have explored the feasibility of localizing parathyroid glands using NIRAF detection with reasonable success, resulting in FDA clearance for this optical technique (14). In this study, we plan to evaluate whether an FDA-cleared device called 'PTeye' (███████████) is beneficial or not, for the surgeon and patient during parathyroid operations. The results of such a study will help us to understand and assess the true impact of optical modalities such as PTeye on (i) improving the quality and efficiency of parathyroid surgeries and (ii) minimizing risk of postsurgical complications and related expenses.

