2.0 Rationale and Specific Aims

The goal of this study is to assess whether using PTeye – a NIRAF detection modality – can reduce healthcare associated costs after parathyroid surgeries and improve patient outcomes. The specific aims of this study is to determine if PTeye is beneficial or not for (i) intraoperative identification of parathyroid tissues, (ii) improving efficiency of parathyroid surgeries, and (iii) minimizing risk of postsurgical complications.

By being able to quickly and definitively locate parathyroid glands while in the operating room, the duration of surgical procedure could be further reduced. In addition, the number of frozen section biopsy (or PTH aspirate) and associated costs can be minimized. Furthermore, repeat surgeries as a result of missing a diseased parathyroid gland at the time of the initial parathyroidectomy for hyperparathyroidism could potentially be avoided.

Primary Outcome Measure:

1. Number of frozen sections (or PTH aspirate) sent for analysis
 - a. Number of frozen sections (or PTH aspirate) sent for analysis during the procedure to confirm potential parathyroid tissue [Time Frame: Immediate. During PTx procedure.]

Secondary Outcome Measure:

1. Persistent hyperparathyroidism (Immediate)

- a. Failure of intra-operative parathyroid hormone (PTH) to normalize (defined as failure of PTH to drop > 50% of its baseline value at final intra-operative PTH assay and/or failure of PTH to drop < 65 pg/ml or 6.9 pmol/L). [Time Frame: During parathyroidectomy (PTx) procedure]
- 2. Persistent hyperparathyroidism or hypercalcemia (transient)
 - a. Elevated blood calcium levels (total blood calcium level > 10.5 mg/dL or 2.6 mmol/L) with/without elevated parathyroid hormone (PTH) (serum intact PTH > 65 pg/ml or 6.9 pmol/L) at first postoperative visit. [Time Frame: 5-14 days after PTx procedure]
- 3. Persistent hyperparathyroidism or hypercalcemia (failed parathyroidectomy)
 - a. If blood calcium with/without parathyroid hormone (PTH) has not normalized at 1st post-operative visit, calcium and/or PTH is subsequently measured as necessary. Patient is defined to have a failed parathyroidectomy if hypercalcemia/hyperparathyroidism (defined as total blood calcium level > 10.5 mg/dL or 2.6 mmol/L, with/without elevated serum intact PTH > 65 pg/ml or 6.9 pmol/L) persists at or after the 6th postoperative month. [Time Frame: 6 months after PTx procedure]
- 4. Overall number of parathyroid glands identified

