 - a. Overall number of parathyroid glands identified (Experimental Group: Glands identified with naked eye + NIRAF; Control Group: Glands identified with naked eye) [Time Frame: Immediate. During PTx procedure.]
- 5. Number of parathyroid glands identified with NIRAF
 - a. Number of parathyroid glands identified with NIRAF, which was not seen with surgeon's naked eye [Time Frame: Immediate. During PTx procedure.]
- 6. Number of diseased parathyroid glands identified versus preoperatively localized glands
 - a. Number of diseased parathyroid glands identified intra-operatively versus glands localized preoperatively using sestamibi, CT or ultrasound [Time Frame: Preoperative to immediate during PTx procedure.]
- 7. Number of intra-operative parathyroid hormone (PTH) assays sent
 - a. Number of intra-operative parathyroid hormone assays sent during the procedure [Time Frame: Immediate. During PTx procedure.]
- 8. Duration taken to identify first parathyroid gland
 - a. Duration taken to identify 1st parathyroid gland in PTx procedure – timed from skin incision to finding PG. [Time Frame: Immediate. During PTx procedure.]
- 9. Duration taken to identify last parathyroid gland
 - a. Duration taken to identify last parathyroid gland in PTx procedure – timed from skin incision to finding the last PG. [Time Frame: Immediate. During PTx procedure.]
- 10. Duration of parathyroidectomy (PTx) procedure
 - a. Duration of PTx procedure – timed from skin incision until the surgeon notifies the anesthesia team to awaken the patient [Time Frame: Immediate. During PTx procedure.]
- 11. Duration taken for intraoperative parathyroid hormone (PTH) to normalize
 - a. Time taken for PTH to attain cure criteria or normalize - timed from skin incision until the PTH levels drops > 50% of its baseline value and/or PTH drops < 65 pg/ml or 6.9 pmol/L. [Time Frame: Immediate. During PTx procedure.]
- 12. Number of nights spent in the hospital after parathyroidectomy
 - a. Number of nights spent for postoperative recovery in the hospital after the surgical procedure. [Time Frame: 0-72 hours after PTx procedure.]
- 13. Number of 'false positive' tissues excised by surgeon
 - a. Number of tissues that were excised by surgeon assumed to be parathyroid tissue, but is later validated as nonparathyroid tissue (false positive) by histology [Time Frame: Immediate to 10 days after PTx procedure.]
- 14. Number of doctor visits/emergency department visits or hospital admissions

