5.0 Enrollment/Randomization

The research will be designed as a single center study, where patient recruitment will be conducted by the participating surgeon at UCSF. The initial evaluation will be conducted while the surgeon is evaluating the patients. The final eligibility of each patient for participating in this study will be determined by the participating surgeon in accordance of his/her medical conditions. Following the exclusion criteria, the study will aim to accrue all eligible patients who are going to the OR as part of their standard surgical procedure.

All participants must be provided a consent form describing the study with sufficient information for each participant to make an informed decision regarding their

participation. Participants must sign the IRB-approved informed consent form prior to participation in any study specific procedure. The participant must receive a copy of the signed and dated consent document. The original signed copy of the consent document must be retained in the medical record or research file.

1. On the date of procedure consent at clinic or the date of surgery, patients will be given a paper consent form detailing about the outcome study with PTeye in addition to the consent for the surgical procedure that will be performed.
2. The key study personnel will briefly describe the PTeye and its application to the patient.
3. If the patient is interested in participating, the key study personnel will provide the patient with a paper-based consent form.
4. The key study personnel or the surgeon assigned to the patient will be available to discuss the protocol with the patient (including, risks, benefits, alternatives, etc.). The patient will also be provided with the contact information of the principle investigator should they have any questions.
5. If the patient consents to be part of the study, a scan of their signed consent form will be stored digitally in the patient's medical record.

Prior to surgery, the patient will be assigned a unique ID (e.g. Para_001). The unique ID will be utilized for randomly allocating the patient to the experimental arm (where the surgeon will use PTeye) or a control arm (where the surgeon will not use PTeye). The allocation will be conducted by the study coordinator using 'Random Allocation Software' (<http://mahmoodsaghaei.tripod.com/Softwares/randalloc.html>).

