10.0 Statistical Considerations

Currently there are no comparable published randomized trials that have evaluated the effect of NIRAF detection for reducing intraoperative frozen section analysis (or PTH aspirate) during parathyroidectomies. Based on preliminary data obtained from a similar ongoing study at Vanderbilt University Medical Center over 123 patients, an 83% reduction in frozen section analysis was observed in the interventional group of 63 patients where NIRAF was used, compared to the control group of 60 patients where NIRAF was not used (unpublished). The mean frozen section analysis (FSA) obtained for the NIRAF group is 0.1 FSA/patient versus 0.6 FSA/patient obtained in the control group. Assuming, that an expected mean difference of 0.6 FSA/patient needs to be observed between the NIRAF and the control group, where the standard deviation of the enrolled study population is 0.8 (Standard Deviation obtained in VUMC study population is 0.78 FSA/patient), 47 patients would be required per group (for a 95% powered study). Since this study may involve patient follow-up for data up to 6 months after surgery, we will thus assume an approximate data attrition rate of 15%, thus requiring a recruitment of 55 patients per group. Therefore, a total of 110 patients (study and control arm) should be recruited per surgeon for this study at this study site. Overall, 110

patients need to be enrolled at this study site under a single surgeon to assess the impact of this technology.

Sample size	
2-side significance level	0.05
Power (1-beta)	0.95
Ratio of sample size, Control/NIRAF group	1
Expected mean in NIRAF group	0.7
Expected mean in Control group	0.1
Study population standard deviation	0.8
Result	
Sample Size - Control group	47
Sample Size - NIRAF group	47
Sample Size – Control group compensated for 15% attrition	55
Sample Size – NIRAF group compensated for 15% attrition	55
Total sample size	110

Analysis Plan:

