Continuous variables will be reported using medians and interquartile ranges (IQRs). Categorical variables will be reported using counts, percentages, and their 95% confidence intervals (CIs). Comparisons of the NIRAF and control parathyroidectomy groups for primary and secondary outcomes will be done using (a) 1-sided χ^2 or Fisher tests for categorical variables and (b) 2-tailed Student's t-test or Wilcoxon's test for continuous variables (depending on distribution of data). To analyze factors that influence the primary outcome assessed for this study, i.e., number of frozen sections specimens (or PTH aspirate) sent for analysis, a generalized linear mixed models will be used. The following variables will be considered as fixed effects for the study model: (i) nature of the intervention (NIRAF or control), (ii) age, (iii) BMI, (iv) number of intraoperative PTH assays, (v) number of diseased parathyroid glands seen, and (vi) type of parathyroid surgery (focused parathyroidectomy or bilateral neck exploration). The multivariate analysis based on this model will generate the respective odds ratios and their 95% CIs for the aforementioned factors that are being considered. A p-value ≤ 0.05 based on the statistical analysis for continuous/categorical variables under the primary and secondary outcomes measured in this study will be considered as significant.

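### The adjusted model for frozen sections conditions on two counts made during surgery, so its intervention odds ratio may not be the total device effect

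*Combined protocol and SAP*

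**What the plan says.** Section 10.0 (Analysis Plan) sets two analyses for the primary outcome. One is a between-arm comparison without covariates, by t-test or Wilcoxon test. The other is a generalized linear mixed model, introduced as a way to study what influences the number of frozen sections (or PTH aspirates). Its fixed effects are the intervention, age, BMI, "iv) number of intraoperative PTH assays, (v) number of diseased parathyroid glands seen", and type of parathyroid surgery. On reporting, "The multivariate analysis based on this model will generate the respective odds ratios and their 95% CIs" for all these factors, the intervention included.

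Section 5.0 fixes the time order: "Prior to surgery, the patient will be assigned a unique ID", and that ID is then used for random allocation.

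Section 2.0 lists both counts among the secondary outcomes. Outcome 7 is "Number of intra-operative parathyroid hormone assays sent during the procedure". Outcome 6 is "Number of diseased parathyroid glands identified intra-operatively versus glands localized preoperatively using sestamibi, CT or ultrasound".

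The plan does not say that the model's intervention term is conditional on events during the operation. It plans no model restricted to baseline covariates.

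**The concern.** A variable measured after allocation can itself be changed by the treatment. Holding it fixed can do two things. It removes whatever part of the treatment effect passes through that variable. It can also create a spurious effect when an unmeasured factor, here case difficulty, drives both the variable and the outcome.

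The protocol itself gives a route for diseased glands seen. Section 1.0 says "Inability of the surgeon to identify or localize the diseased PG can occur" in 5–10% of cases, and Section 2.0 expects that "repeat surgeries as a result of missing a diseased parathyroid gland at the time of the initial parathyroidectomy" could be avoided with the device. The number of diseased glands a patient has is a baseline feature, but the number seen depends on detection, which is what the device is meant to improve. For PTH assays the documents state no expected direction, but the trial sets out to compare them between arms.

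At stake is the reported size of the benefit. The t-test or Wilcoxon test yields a p-value, and continuous variables are summarised by medians and IQRs. The model's odds ratio is therefore the only device-effect estimate with a 95% CI that the plan specifies for the primary outcome.

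**Working it through.** **1. The plan's own figure.** Section 10.0 gives a difference of 0.6, SD 0.8, two-sided 0.05 and power 0.95.

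n per group = 2(1.960 + 1.645)² × 0.8² / 0.6² = 46.2, rounded up to 47. For attrition, 47 × 1.15 = 54.05, rounded up to 55, and 2 × 55 = 110. The stated figures reproduce. No covariate enters, so the sample size is not touched by this point.

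**2. Timing and role of each fixed effect.**

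| Fixed effect | Known before allocation? | Also a trial outcome? |
|---|---|---|
| Age, BMI | Yes | No |
| (iv) PTH assays | No, counted during surgery | Yes, secondary outcome 7 |
| (v) Diseased glands seen | No, counted during surgery | Yes, intraoperative part of secondary outcome 6 |
| (vi) Type of surgery | Only if it means the planned approach; not stated | No |

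**3. Effect passing through the covariate (illustration; all parameters assumed).** Let assays M be Poisson with mean 2 in controls and 2r in the device arm. Let the log rate of frozen sections rise by γ per assay, with no other device effect. The total rate ratio is exp[2(r − 1)(e^γ − 1)]. Given M, the rate ratio is exactly 1.

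| r | γ | Total rate ratio | Assay-adjusted |
|---|---|---|---|
| 0.8 | 0.2 | exp(−0.4 × 0.2214) = 0.92 | 1.00 |
| 0.8 | 0.4 | exp(−0.4 × 0.4918) = 0.82 | 1.00 |
| 0.6 | 0.2 | exp(−0.8 × 0.2214) = 0.84 | 1.00 |
| 0.6 | 0.4 | exp(−0.8 × 0.4918) = 0.67 | 1.00 |

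Simulation with 400,000 patients agrees. For any frozen section, the unadjusted odds ratios are 0.90 to 0.67 and the adjusted ones about 1.00. A real benefit of this kind would vanish from the model.

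**4. Shared cause (illustration).** U ~ N(0,1) is unmeasured difficulty and z = 1 for the device arm.
- Frozen sections ~ Poisson(0.6 · RR^z · exp(0.7U − 0.245)).
- Assays ~ Poisson(3.0 · r^z · exp(0.4U − 0.08)).
- Diseased glands seen = 1 + Bernoulli(expit(−1.5 + U)), a control mean of 1.22. In the device arm one more gland is added with mean probability 0, 0.05 or 0.10, proportional to that same probability.

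Only the 0.6, the ratio 0.1/0.6 used below and the 5–10% scale for glands come from the documents. The rest is assumed. The fit is a Poisson model with robust standard errors, on 400,000 patients per scenario. Rate ratios are used because, unlike odds ratios, they do not move merely because a covariate is added. With RR = 1.00:

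| Device shift | Adjusted rate ratio |
|---|---|
| None | 1.00 |
| Assays −10% / −20% | 1.06 / 1.13 |
| Assays +10% / +20% | 0.94 / 0.90 |
| Glands +0.05 / +0.10 | 0.97 / 0.95 |
| Assays +20% and glands +0.10 | 0.85 |
| Assays −20% and glands +0.10 | 1.06 |

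Unadjusted estimates stay at 0.99–1.00. Repeat runs agree to within about 0.01.

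False-positive rates of the adjusted term at 110 patients (nominal 5%; 1,000 simulated trials unless noted) vary somewhat between runs:
- assays −20%: 7.0–8.5%
- assays +20% and glands +0.10: 9.9–10.5%
- assays −20% and glands +0.10: 6.7% (5,000 trials)
- no shift: 5.8–6.8%

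The t-test gave 5.1–5.5% and Wilcoxon 5.3%. Part of the excess in the adjusted term is therefore small-sample behaviour of the robust standard error, not conditioning.

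**5. At the preliminary means.** Section 10.0 gives "0.1 FSA/patient versus 0.6 FSA/patient obtained in the control group", so RR = 0.1/0.6 = 0.167. Across the shifts the adjusted estimate runs from 0.140 to 0.188, a reduction of 86% to 81% against 83%. Rejection is 98–99.8% for the adjusted term and 98–99% for the planned tests. The simulated SD is 0.73, against the 0.78 reported for the preliminary data.

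**The case against.** The strongest reply is that the plan already contains a clean comparison, and that the model is presented as a study of influencing factors, where intraoperative variables belong. This stands in part: the t-test or Wilcoxon comparison does address the total effect. But the intervention is the first factor listed, it receives an odds ratio with a CI, and nothing marks that estimate as exploratory or conditional.

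The harm is also conditional and may be small. No document gives a device shift in assays or glands. At the preliminary effect, the simulated standard error of the adjusted log rate ratio is about 0.47, so a 95% CI around 0.167 spans roughly 0.167 × exp(±1.96 × 0.47), or 0.07 to 0.42. The range 0.140–0.188 lies well inside it. Shifts can also offset each other: fewer assays with more glands seen gives 1.06, and that pairing fits the stated aims of efficiency and identification at least as well as the reinforcing one. Using 5–10% as the gland shift is generous, since its upper end assumes the device recovers every missed case. All of this stands and limits the size. It does not make the estimate the total device effect.

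A last objection is that removing the two counts outright would discard a legitimate factor analysis. That is fair, and a labelled exploratory model keeps it.

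**Conclusion.** The concern holds. Two fixed effects in the adjusted model for the primary outcome are measured after allocation and are themselves trial outcomes, so its intervention odds ratio may not be the total device effect. That much follows from the text and is not in doubt.

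The size is uncertain. Through shared causes, a true rate ratio of 1.00 could be reported as anything from 0.85 to 1.13 under the assumed shifts. An effect acting only through assays would be removed entirely. At the effect seen in the preliminary data, the significance conclusion survives and only the reported size moves. These figures rest on assumed assay and gland means, difficulty coefficients and device shifts, and they are rate ratios, not the planned odds ratios. If the device shifts neither count, there is no such bias. The point should be fixed before the data are analysed, but it does not undermine the main between-arm test.

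**What to change.** In Section 10.0 (Analysis Plan):

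- Estimate the adjusted device effect on the number of frozen sections without (iv) and (v), using only variables fixed before allocation: age, BMI and, optionally, first versus repeat parathyroid surgery, which eligibility makes known.
- Keep (vi) only if it is defined as the approach planned before allocation.
- If the model with (iv) and (v) is still wanted, label it an exploratory factor analysis and state that its intervention term will not be interpreted as the device effect.

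The cost is analysis-plan wording. If (vi) is kept, the planned approach must be recorded before allocation where it is not already captured. The sample size and the unadjusted tests do not change.

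### Type of surgery is modelled only for frozen sections; gland count, time to last gland and operating time are compared unadjusted, which is valid but gives up precision that one pre-allocation field would recover

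*Combined protocol and SAP*

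**What the plan says.** All secondary outcomes share one testing sentence in the Analysis Plan (section 10.0): "Comparisons of the NIRAF and control parathyroidectomy groups for primary and secondary outcomes will be done using" chi-square or Fisher tests for categorical variables, and a t-test or Wilcoxon test for continuous ones. No covariate is mentioned.

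The only model with covariates has a restricted purpose: "To analyze factors that influence the primary outcome assessed for this study, i.e., number of frozen sections specimens (or PTH aspirate) sent for analysis". Its sixth fixed effect is "vi) type of parathyroid surgery (focused parathyroidectomy or bilateral neck exploration".

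Three secondary outcomes in section 2.0 are likely to depend on the extent of the operation:

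- Outcome 4: "Overall number of parathyroid glands identified (Experimental Group: Glands identified with naked eye + NIRAF; Control Group: Glands identified with naked eye".
- Outcome 9, time to last gland: "timed from skin incision to finding the last PG".
- Outcome 10, procedure duration: "timed from skin incision until the surgeon notifies the anesthesia team to awaken the patient".

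On allocation, section 5.0 says "The unique ID will be utilized for randomly allocating the patient to the experimental arm" or the control arm, using a software tool. It names no stratification factor. Section 4.0 does not limit eligibility to one surgical approach and admits repeat operations. The list of data to be compiled in section 6.0 does not include type of surgery.

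**The concern.** A focused operation is directed at a target gland, whereas a bilateral exploration looks on both sides of the neck. It follows from the terms that approach bears on how many glands are found, when the last one is found and how long surgery takes. The sponsor already treats approach as relevant to frozen sections, where the link is less direct.

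Pooling the two kinds of operation without adjustment leaves variation unrelated to the device in the error term. It also leaves any chance difference in case mix between arms in the point estimate. Specific aims (i) identification and (ii) efficiency in section 2.0 rest largely on outcomes of this kind, so wider intervals than necessary weaken what the trial can say about those aims.

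**Working it through.** **The plan's own figure.** For the primary outcome, n per group = 2 × [0.8 × (1.960 + 1.645) / 0.6]² = 46.2, rounded up to 47, as stated. With 15% attrition, 47 × 1.15 = 54.05, or 55 rounded up (47 / 0.85 = 55.3). The point does not depend on these figures. I use 55 per arm, because outcomes 4, 9 and 10 are recorded during surgery and the attrition allowance is for 6-month follow-up.

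**General precision gain.** The documents give no variance for these outcomes, so let R² be the assumed share of variance explained by type of surgery. Detectable difference at 80% power, two-sided 0.05, in units of total SD:

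(1.960 + 0.842) × √[2(1 − R²)/55]

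| R² | Detectable difference (SD) | Power for the effect with 80% power unadjusted | Equivalent n per arm, 55/(1 − R²) |
|---|---|---|---|
| 0 | 0.53 | 80% | 55 |
| 0.1 | 0.51 | 84% | 61 |
| 0.2 | 0.48 | 88% | 69 |
| 0.3 | 0.45 | 92% | 79 |
| 0.4 | 0.41 | 95% | 92 |
| 0.5 | 0.38 | 98% | 110 |

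The noncentral t gives 0.54 in place of 0.53 in the first row. With 47 per arm the range is 0.58 falling to 0.55-0.41.

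**Duration (outcome 10).** Assumptions: bilateral operations 20-40 min longer, within-type SD 20-30 min, 30-50% bilateral, and a true saving of 10 min. Total variance = SD² + p(1 − p) × gap². Power is from the noncentral t and is paired within each scenario:

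| SD | Gap | Share bilateral | R² | Unadjusted | Adjusted | Gain (points) |
|---|---|---|---|---|---|---|
| 30 | 20 | 30% | 9% | 38% | 41% | 3 |
| 30 | 20 | 50% | 10% | 38% | 41% | 3 |
| 30 | 40 | 30% | 27% | 31% | 41% | 10 |
| 30 | 40 | 50% | 31% | 30% | 41% | 11 |
| 20 | 20 | 30% | 17% | 66% | 74% | 8 |
| 20 | 20 | 50% | 20% | 64% | 74% | 10 |
| 20 | 40 | 30% | 46% | 48% | 74% | 26 |
| 20 | 40 | 50% | 50% | 45% | 74% | 29 |

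For example, the last row has total variance 400 + 0.25 × 1600 = 800, so R² = 400/800 = 50%.

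**Gland count (outcome 4).** Assume mean glands of 1.2-2.0 in focused and 3.5-3.6 in bilateral operations (a gap of 1.5 to 2.4), a within-type SD of 0.5-0.7 and 30-50% bilateral. R² is then 49-85%, and the detectable difference (0.539 × SD) falls from 0.46-0.75 to 0.27-0.38 glands. If the device added 0.4 glands in both types, adjusted power would be 84-99%. If it added 0.4 only in bilateral cases, the average gain would be 0.4 × 0.3 = 0.12 to 0.4 × 0.5 = 0.20 glands, and adjusted power only about 15-55%.

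**Chance imbalance.** The SD of the between-arm difference in bilateral share is √[2p(1 − p)/55] = 0.087 (p = 0.3) to 0.095 (p = 0.5), a 95% range of about ±17 to ±19 points. With a 30 min gap this shifts the unadjusted difference by up to 5.1-5.6 min; with a 2-gland gap, by 0.34-0.37 glands.

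**Type I error of the unadjusted t-test.** Simulation (40,000 trials per setting, R² 0.2-0.4, 30% or 50% bilateral) gives 4.6-5.0% overall. Among trials with an imbalance of at least 15 points it is 12-23%. Such imbalance occurs in 7-10% of the simulated trials, or 9-12% by normal approximation.

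**The case against.** The strongest reply is that this is a preference for efficiency. In a randomised comparison an unadjusted test is valid, the outcomes are secondary, and the primary outcome already has a model containing type of surgery. That stands, and it sets the weight of the point.

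Lost precision and chance imbalance are also largely one cost seen from two sides, because the unadjusted standard error already includes variation from random case mix. They should not be added together.

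A reader might infer more than the documents support:

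- *That the planned tests are invalid.* They are not: overall type I error is about 5%. The excess appears only conditionally, in the minority of trials with marked imbalance.
- *That imbalance could be as large as the effect sought.* The documents state no target effect for these outcomes. Against the effects assumed here, the 95% extreme is 5-6 min against 10 min, and 0.34-0.37 against 0.4 glands. Neither reaches the effect.
- *That type of surgery dominates operating time.* Even under the assumptions above, 50-91% of the variance in duration lies elsewhere.
- *That gland-count power would certainly reach 84-99%.* That needs the same gain in both types of operation, which is doubtful if a focused operation aims at one gland.
- *That time to first gland (outcome 8) is equally affected.* How many further glands are sought does not obviously change when the first is found, and nothing in the documents links the two.

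**Conclusion.** The point holds as a cheap improvement to secondary outcomes 4, 9 and 10. The text is clear: type of surgery enters only the frozen-section model, these outcomes are tested unadjusted, and no stratification by approach is named.

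The gain rests on assumptions, because the documents give no SD, case mix or effect size for these outcomes. It is modest if approach explains about 10% of the variance (0.51 SD detectable) and substantial if it explains half (0.38 SD). For duration the paired power gain runs from 3 to 29 points. For gland count the share explained may be larger, but the gain depends on the within-type SD and on whether the device works equally in both types of operation. No separate figure is available for time to last gland; only the general R² table applies.

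**What to change.** Record the planned approach (focused or bilateral) for every patient before allocation. State in the Analysis Plan that outcomes 4, 9 and 10 will be analysed with a model on arm plus planned approach, linear or, for skewed times, log-linear. Report the adjusted difference between arms with its 95% CI; the plan at present promises intervals only for categorical variables and for the model's odds ratios. If a rank test is kept, use the van Elteren test stratified by planned approach. Show results within each planned approach descriptively.

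Do not adjust for the approach as performed. The device may change it, and adjustment could then remove part of the device's effect. Section 10.0 does not say whether its covariate is the planned or the performed approach, so this needs stating.

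The cost is one new pre-allocation data field, since section 6.0 does not list it, a sentence or two in the Analysis Plan, and slightly more analysis work. N stays at 110. The choice should be fixed before outcome data are seen, because a later adjustment would look post hoc.
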